5. **PHQ:** We have chosen to identify major psychopathology using the PRIME-MD Patient Health Questionnaire [74]. This questionnaire consists of nine questions that screen for depression. Each item yields a score of 0-3, and the highest possible total score for all items is 27. The scale can be used longitudinally to identify trends in depressed mood. Subjects with evidence of suicidal ideation or any other severe, acute psychiatric symptom (e.g., psychosis) will be excluded from the study. Subjects who answer “more than half the days” to 5 or more items will be excluded from the study. Since the questionnaire relies on patient self-report, all responses will be verified by the principal investigator, if a subject answers “more than half the days” to 5 or more items to confirm exclusion is warranted.
6. **Self-efficacy questionnaires:** Evaluates confidence to resist smoking across a number of different situations [60]. The scale yields a total score, as well as subscores for positive & negative affect situations, and habit/craving items. This scale has been a strong predictor of smoking outcomes in previous studies [73].
7. **Exhaled carbon monoxide measurement.** Subjects will be asked to blow into a machine that measures CO in parts per million (ppm). Levels <9 ppm are consistent with cigarette abstinence [69].
8. **Urine sample:** A urine sample will only be collected at BL, V2, V5, and V6 and analyzed only if serum can not be obtained. Urine will be tested using the NicAlert method.

The screening visit is expected to take 1.5 hours. The participant will be given a handout to record cigarette intake prior to subsequent study visits.

Study Procedures and who will perform them:

Baseline: Eligible subjects scheduled to return for a baseline (i.e. randomization) visit approximately 1 week after screening (+ 14 Days). The study nurse will review the patient's medical history and confirm current medical and pregnancy history. She will discuss each case with the study obstetrician (at the performance site) who will sign off on entry of subject into the study.

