- 4) **Medication adverse events:** a) inhaler adverse effects---To minimize potential adverse effects of the inhaler we will a) instruct subjects on proper usage; b) inform subjects to stop medication use 6 weeks after the quit date if they have not completely quit smoking. c) procedure to minimize the risk of increased nicotine exposure--- Although cotinine concentrations are not typically measured during smoking cessation trials, pregnant women are considered a vulnerable population who may be at risk for adverse effects from nicotine. Therefore we would like to ensure that subjects do not receive increased overall nicotine exposure from the nicotine inhaler than is usually obtained from smoking. As stated in the consent we recommend that subjects quit smoking completely when they start inhaler use. Serum cotinine concentrations will be collected at baseline (i.e., while smoking), and at visit 2 (approximately 1-2 weeks after inhaler use). After sample collection of serum from baseline and visit 2, these samples will be sent out for analyses to Yale University where samples will be analyzed on a weekly basis (see attached letter of support). The R.N. responsible for ongoing patient care at each site will keep a log of cotinine concentrations for each subject while smoking and while on nicotine or placebo inhaler. Subjects will be notified immediately by the R.N. if their cotinine concentrations obtained at visit 2 exceeds concentrations obtained while smoking. A serum cotinine concentration while on treatment that exceeds a subject's baseline or screening smoking levels by 40% will be considered an increase in overall nicotine exposure. Please note that this is a conservative approach because the normal individual variation of serum cotinine in pregnant women who continue to smoke is 30% (Oncken, et al 1996). If a subject is notified to decrease her inhaler use accordingly (or completely quit smoking if she is not totally abstaining from cigarettes). A repeat cotinine concentration will be repeated within a week on the new dosage regimen. If the repeat cotinine is elevated compared to baseline values as described above, the medication will be stopped. It is also noteworthy that we are examining an intermittent nicotine delivery system in this study in an attempt to minimize nicotine exposure. It would be difficult for a subject to smoke and use the inhaler at the same time, so we anticipate that nicotine exposure will not exceed baseline levels while smoking. Also, if a subject clinically significantly increases her smoking while on treatment [ie., 1) she stopped smoking at visit 2 using the inhaler, but starts smoking at a later visit and continues to use the inhaler or 2) if she increases the average number of cigarettes per day over the previous 7 days by 25% compared to visit 2], we will perform a repeat cotinine test at the visit where this is identified. A significant change in smoking patterns and/or inhaler use will be decided by the research nurse. If this cotinine test is elevated compared to baseline levels, the elevated cotinine will be handled as above. Subject's who discontinue the study early will be asked to return the inhaler, including any unused cartridges, and no inhalers will be dispensed to the subject from this point.

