
If for any reason we are unable to obtain blood for serum cotinine, overall nicotine exposure will be assessed with the nicalert urine test at each visit. With this system there are 5 levels of exposure (Level 0: 1-10, Level 1: 10-30, Level 2: 30-100, Level 3: 100-200, Level 4: 200-500, Level 5: 500-1000, and Level 6 1000 plus) and an increase in any

Nicotine Replacement for Smoking Cessation during Pregnancy

level would be consistent with an increase in exposure. This type of monitoring was utilized in one clinical trial that was monitored by the FDA to estimate overall nicotine exposure in pregnant women (33).

- 5) **Pregnancy adverse problems**--We are only including subjects with chronic stable medical problems and no imminent pregnancy problems will be enrolled into the study. If there are any questions regarding current pregnancy problems the case will be discussed with the primary care provider (after obtaining consent from subject) and also reviewed with study obstetricians. We are monitoring nicotine exposure in both groups which may decrease the risk of adverse pregnancy problems. Additionally, women receive a comprehensive behavioral intervention designed to help them quit smoking, which should decrease the risk of pregnancy adverse effects. Women are monitored closely throughout the study and if an adverse event occurs consultation and treatment will be coordinated with their obstetrician.
- 6) **Withdrawal and worsening mood symptoms**-- although uncomfortable, nicotine withdrawal symptoms (irritability, craving for cigarettes, insomnia, increased appetite/weight gain, depressed mood) do not propose a significant medical risk. Nicotine replacement is designed to relieve withdrawal symptoms. Some studies suggest that especially persons with a history of depression may be at an added risk of depression with smoking cessation; however, we did not observe this in our last study (Oncken et al., 2008). If depressive symptoms occur (as evidenced by patient report or worsening symptoms on the beck questionnaire), the subject will be seen by a masters level counselor or [name]. [name] will help devise the treatment plan. Subjects who experience significant increases in depressed mood will be referred for further evaluation and treatment.

3. Describe circumstances that may lead to a subject being removed from the trial by the PI, e.g. due to failure to follow study procedures, and the process for doing so:

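### The urine back-up for cotinine cannot detect a rise in nicotine exposure in a woman whose reference NicAlert reading is already at the open-ended top level

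*Combined protocol and SAP*

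**What the plan says.** The serum rule is in Appendix A, item 2.B.4 (medication adverse events). An on-treatment serum cotinine that "exceeds a subject's baseline or screening smoking levels by 40% will be considered an increase in overall nicotine exposure". The woman is then told to cut down her inhaler use, or to stop smoking if she has not, and the test is repeated. "If the repeat cotinine is elevated compared to baseline values as described above, the medication will be stopped".

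The urine back-up follows in the same item: "If for any reason we are unable to obtain blood for serum cotinine, overall nicotine exposure will be assessed with the nicalert urine test". The scale is introduced with "With this system there are 5 levels of exposure" and set out as "Level 0: 1-10, Level 1: 10-30, Level 2: 30-100, Level 3: 100-200, Level 4: 200-500", then "Level 5: 500-1000, and Level 6 1000 plus) and an increase in any" "level would be consistent with an increase in exposure". No unit is attached to the bands. The text does not name the visit against which a rise is judged, and it does not restate what follows from a rise.

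The main protocol (Screening Procedures, item 8) has urine collected at baseline and Visits 2, 5 and 6, and analysed only when serum is unavailable. It names one method: "Urine will be tested using the NicAlert method". Appendix A, by contrast, speaks of strip testing at every visit.

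**The concern.** A criterion based on moving up a level needs a level to move up to. Level 6 is unbounded and is the last one, so for a woman who starts there the rule has no way of firing.

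The serum steps (notification, reduced use, repeat test, stopping study medication) all begin with a detected increase. If they are meant to follow the urine result too, as seems intended, a woman at Level 6 can never enter that sequence on urine alone. The stated aim of item 2.B.4 is that no woman should receive more nicotine overall than she usually gets from smoking. For this subgroup the back-up cannot check that aim.

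**Working it through.** The plan gives no figure to reproduce. The check applies the printed bands to the printed criterion.

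**Inputs.** The seven NicAlert bands and the rise-in-level criterion (Appendix A, item 2.B.4), and the 40% serum threshold from the same item, used for comparison. Adjacent bands share an endpoint, so I place each boundary value in the higher band. The reference is taken to be the baseline reading, by analogy with the serum rule.

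**Level 6.** Take starting values of 1000, 1500, 2000 and 5000, and multiply each by 1.4, 2, 5 and 10. All 16 results lie between 1400 and 50,000, so all remain at Level 6 and the criterion fires in 0 of 16. This holds by construction: any value of 1000 or more, multiplied by any factor above 1, is still 1000 or more.

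**Levels 0 to 5.** For a band from L to U:
- the limit on a rise that can go unseen is U/L (a rise from L that stops just short of U);
- a 40% rise crosses into the next band only if the starting value is at least U/1.4;
- if starting values are assumed log-uniform within the band, the share for which a 40% rise is seen is ln(1.4)/ln(U/L).

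| Level | Band | U/L | U/1.4 | Share of 40% rises seen (assumed log-uniform) |
|---|---|---|---|---|
| 0 | 1–10 | 10 | 7.1 | 15% |
| 1 | 10–30 | 3 | 21.4 | 31% |
| 2 | 30–100 | 3.3 | 71.4 | 28% |
| 3 | 100–200 | 2 | 142.9 | 49% |
| 4 | 200–500 | 2.5 | 357.1 | 37% |
| 5 | 500–1000 | 2 | 714.3 | 49% |
| 6 | 1000 and over | no limit | none | 0% |

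For example, 550 to 990 is a rise of 80% (990/550 = 1.80) and stays in Level 5. Conversely, 990 to 1001 is a rise of 1.1% (1001/990 = 1.011) and counts as an increase.

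**Does another provision close the gap?**
- The 40% rule needs a serum value, which these women lack at the visit in question.
- A clinically significant increase in smoking on treatment (item 2.B.4) prompts only a repeat cotinine test compared with baseline. If blood is still unobtainable, that test is the strip again, with the same ceiling.
- If Visit 2 is missed, the blood draw moves to the next scheduled visit (Baseline, item 2). This covers a missed visit. It does not cover a visit that is attended but yields no blood.
- No quantitative urine assay is described. The gas chromatography/mass spectrometry method is described for serum.

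**Choice of reference visit.** If the criterion is read visit to visit, a woman who drops below Level 6 and returns to it could trigger it. A woman at Level 6 at the comparison visit still could not.

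**The case against.** The strongest reply is that this is a narrow ceiling effect in a back-up tool. Serum is the primary measure, drawn at baseline and Visits 2, 5 and 6. Cartridges, diaries, exhaled CO and the Nicotine Use Survey are reviewed at Visits 1 to 6, and women still smoking at week 6 come off medication. The documents also give reasons to expect rises to be uncommon: inhaler exposure of roughly 60% of that from smoking (section A.2.c) and mean replacement of 66% in the six-woman pilot. Finally, the protocol refers to a data and safety monitoring plan for cotinine monitoring, and that plan is not among the documents supplied.

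Much of this stands. It limits how often the gap would matter, and only the supplied text can be called silent on a Level 6 reference. It does not remove the gap. None of the other checks is a cotinine trigger, average replacement says little about an individual who smokes and uses the inhaler, and the plan sets up monitoring despite expecting exposure not to exceed baseline.

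A reader might infer that an unchanged Level 6 will be logged as reassurance and so mislead the DSMB. The documents do not say so. The urine criterion runs one way only, the nurse's log holds cotinine concentrations, and the one DSMB table described (Appendix A, item 4) covers serious adverse events. Nor is the rule aimed at the most heavily exposed women as a group: its purpose is a comparison of each woman with her own smoking level.

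**Conclusion.** The point holds in a limited form. For a woman monitored by urine whose reference reading is Level 6, the stated criterion has no ability to detect an increase. This needs no assumption beyond the printed bands and a reference reading at that level. That baseline is the reference, and that the serum steps follow a urine rise, are inferences from the serum rule.

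The number affected cannot be sized. The documents give no urine cotinine distribution, no unit for the bands and no expected rate of missing serum. It is tempting to assume a distribution, but the answer then comes from the assumption. With a lognormal baseline of log-SD 0.7 to 1.0, the share at or above 1000, 1 − Φ(ln(1000/median)/SD), is 16–24% at a median of 500, 50% at 1000 and 66–72% at 1500. That range supports no claim that many women, or few, are affected.

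The primary endpoint, abstinence confirmed by exhaled CO, is untouched. The ceiling is best seen as the extreme of a general mismatch between coarse urine bands and a 40% serum threshold. It merits a correction because following the rule as written can miss the event it exists to find, and the correction is cheap.

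**What to change.** Add to Appendix A, item 2.B.4:
- a Level 6 reference reading makes the comparison not assessable by strip;
- an unchanged Level 6 is not to be read or reported as no increase;
- such women are counted separately in any exposure summary given to the DSMB.

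Where a baseline serum value exists, re-attempt serum at the next scheduled visit, extending the existing provision for a missed Visit 2, so that the serum rule can be applied. Without a baseline serum value a later draw has nothing to be compared with, and the woman stays recorded as unassessed.

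Reconcile the urine criterion with the 40% serum rule and with the data and safety monitoring plan, and name the reference visit and the unit of the bands. In the same edit, settle three inconsistencies: five levels stated against seven listed, shared band endpoints, and urine testing at every visit in Appendix A against collection at baseline and Visits 2, 5 and 6 only in the main protocol. No dose, threshold or stopping rule is proposed here.

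The cost is a few sentences, an occasional additional blood draw, and some women openly recorded as unassessed.

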Aim/Objective 4: To explore mechanisms by which the nicotine inhaler increases birth weight and gestational age.

4. Study Design & Procedures:

Study design: This is a randomized, double blind, placebo-controlled trial of the safety and efficacy of the nicotine inhaler in combination with behavioral counseling for smoking cessation during pregnancy. A total of 360 pregnant smokers will receive nicotine or placebo inhaler medication (1:1 ratio) for 6 weeks followed by a 6-week taper, with double-blind treatment conditions maintained throughout the study. Smoking cessation counseling and medication will be provided by a nurse at each ambulatory clinic. Nurses will be closely supervised by a psychologist with extensive expertise in smoking cessation ([name]), an obstetrician ([name] or [name]), and [name].

Overview of the behavioral intervention: The behavioral intervention, which will be utilized in both arms of the proposed study, exceeds many of the augmented interventions described in the USPHS guidelines [38]. The behavioral counseling will include a 35-minute counseling sessions at each of the first two visits, and 10 minutes of smoking cessation counseling at subsequent visits, delivered by the study nurses.

Overview of pharmacotherapy intervention: We will administer a 6-week course of therapy, consistent with instruction on the package insert. Dosage recommendations are based on the literature and on our pilot data, and will vary according to the level of maternal smoking. Pfizer Pharmaceuticals has agreed to supply us with nicotine inhaler and placebo treatments (see letter of support). To enhance compliance and to confirm patient reports and proper inhaler use, subjects will be asked to keep a daily diary of the number of cartridges used and to return all cartridges at the next study visit. Subjects will be instructed to bring medication and empty cartridges to next visit when they receive their reminder telephone call regarding upcoming appointments. For convenience, subjects will receive a plastic container to transport study drug. At Visit 5 (6 week visit), patients will be instructed on an individualized basis to taper their use over the next 6 weeks. If a study subject does not quit smoking

Nicotine Replacement for Smoking Cessation during Pregnancy

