4. **Exhaled carbon monoxide (CO) measurement and Nicotine Use survey** (which assesses any smoking last seven days and since the last study visit and use of other smoking cessation aids)
5. **Vital Signs** (blood pressure and heart rate) and **Weight** will be obtained.
6. **Adverse Effects Inhaler:** Subjects will rate potential adverse effects (cough, throat irritation, rhinitis, and mouth irritation, which have been noted in other nicotine inhaler studies [6, 40, 66]) on a 4-point scale: 0=absent, 1=mild, 2=moderate, and 3=severe. Other AE's will also be recorded and severity rated. This will be done before the subject is administered treatment so we have a baseline to compare other visits.
7. **Concomitant Medication:** Subjects will be asked about their current medication use, including any prescription medication, over the counter medication, supplement, and/or vitamins.
8. **The Minnesota Nicotine Withdrawal Scale (MNWS)** measures symptoms of tobacco withdrawal on a scale of 0 (not present) to 4 (severe) [24]. We will calculate a total score and a score excluding craving to evaluate withdrawal symptoms during cessation.
9. **Release of Information:** A release of information will be obtained at the baseline visit so the study physicians are able to obtain delivery records if the participant will deliver at a hospital other than HH or BMC.
10. **Counseling:** There are 4 primary goals in the initial counseling session: (1) establishing a rapport with the patient, (2) functional analysis of smoking including a review of self-efficacy in various situations, (3) increasing motivation and confidence to quit smoking (using techniques described in the manual), (4) helping the patient to set and prepare for a quit date.

The study nurse provides 35 min of smoking cessation counseling. Subjects will be given "Need Help putting out that Cigarette?" a booklet available for purchase through the American College of Obstetrics and Gynecology. This booklet is written in English or Spanish, is at a 6th grade reading level, provides information about smoking in pregnancy, and outlines steps to prepare to quit and stay quit during pregnancy. The nurse will use responses to the self efficacy questionnaire and diary to help subjects recognize high-risk situations and develop specific strategies to deal with them. The treatment manual describes four primary sources that influence

Nicotine Replacement for Smoking Cessation during Pregnancy

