Visit 1: Subjects seen approximately 1 week (+/- 4days) after their quit date to assess adverse effects and progress in smoking cessation. At this visit, the nurse administers behavioral counseling (35 minutes) and assesses medication usage. The study coordinator will administer all assessments.

1. Vital signs and weight
2. Exhaled CO measurement
3. Nicotine Use Survey
4. Questionnaires: MNWS
5. Adverse Effects Inhaler & Adverse Events
6. Concomitant Medication
7. Inhaler usage: We will collect used cartridges from patient and review diary of inhaler usage.
8. Counseling: The second counseling session is scheduled 1 week after the quit date. The primary focus of this session will be to assess reactions to the initial session, smoking status, and the effectiveness of the intervention, and to discuss strategies to deal with smoking urges and tobacco withdrawal symptoms. Subsequent sessions will focus on achieving or maintaining abstinence, increasing self-efficacy, skills training (depending on the patient's smoking status), and providing support.

This visit will take 45 minutes.

Visits 2 (2 weeks after the quit date +/- 4 days). The following items will be assessed by research nurse.

1. Vital signs and weight
2. Exhaled CO measurement
3. Maternal Blood draw (15 cc) If possible, this blood draw will be incorporated with other routine prenatal blood draws. Will collect urine as backup.
4. Nicotine Use Survey
5. Questionnaires: MNWS, PHQ
6. Adverse Effects Inhaler & Adverse Events
7. Concomitant Medication
8. Inhaler usage: We will collect used cartridges from patient and review diary of inhaler usage.
9. Dispensement: We will dispense a 2 week supply of study medication, if needed.
10. Counseling (10 Minutes): Counseling will focus on achieving or maintaining abstinence (set another quit date if necessary), increasing self-efficacy, skills training (depending on the patient's smoking status), and providing social support, and using inhaler to combat urges to smoke.

This visit will take 45 minutes. After the session the nurse will send the two maternal serum samples for cotinine analyses. If the visit 2 sample exceeds that of baseline by 40%, the study nurse will call the patient and advise a decrease in inhaler dosage that will be recommended by [name].

Visit 3 (3 weeks after the quit date +/- 4 days). The following items will be assessed by research nurse.

1. Vital signs and weight
2. Exhaled CO measurement
3. Nicotine Use Survey

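### The depression-response rule in Appendix A relies on a Beck questionnaire that no visit schedules; the scheduled depression scale is the PHQ

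*Combined protocol and SAP*

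**What the plan says.** Appendix A, item 2, part B, point 6 (withdrawal and worsening mood) notes that women with a history of depression may be at added risk when they stop smoking. If depressive symptoms occur, "as evidenced by patient report or worsening symptoms on the beck questionnaire", the woman is to be seen by a masters-level counsellor or a named member of the team. The item closes: "Subjects who experience significant increases in depressed mood will be referred for further evaluation and treatment."

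The instrument chosen elsewhere is different. Screening Procedures, item 5, adopts the nine-item PRIME-MD PHQ (maximum score 27) and adds: "The scale can be used longitudinally to identify trends in depressed mood." The lists for Visits 2, 5 and 6 each carry the line "Questionnaires: MNWS, PHQ", and each opens with "The following items will be assessed by research nurse". The table headed Timeline of Study Procedures has a PHQ row and no Beck row.

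Two other places bear on the point. The mediational analyses paragraph in the data analysis section says that depressive symptoms are measured at baseline and at every study visit, but names no scale. The back-up plan after Visit 8 lets staff other than the nurse carry out procedures at Visits 1, 3 and 6.

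**The concern.** A safety rule works only if the measurement that sets it off is actually taken. This rule has two triggers, and one refers to a form that nobody is scheduled to complete. The PHQ is collected three times after baseline, yet the supplied text does not explicitly link a worsening PHQ to the counsellor contact. The only action tied explicitly to PHQ answers is the exclusion at screening.

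At stake is the response to a risk that the protocol itself names, low mood after stopping smoking in pregnant women. A site that follows the sentence literally has no score to check and is left with what the woman reports.

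**Working it through.** There is no figure in the plan to reproduce. The check compares each mention of a depression scale with the visit lists and the table.

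**Denominator.** The section on length of participation gives 10 visits: screening, baseline and Visits 1 to 8. That leaves 10 − 2 = 8 after baseline.

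| Measure | Visit lists in the text | Table of study procedures |
|---|---|---|
| Beck scale | 0 of 10 | 0 of 10 |
| PHQ | Screening, Visits 2, 5, 6: 4 of 10 | Screening, baseline, Visits 2, 5, 6: 5 of 10 |
| PHQ after baseline | 3 of 8 | 3 of 8 |
| MNWS | Baseline, Visits 1–6: 7 of 10 | Baseline, Visits 1–5: 6 of 10 |
| Adverse events after baseline | Visits 1–6: 6 of 8 | Visits 1–6: 6 of 8 |

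**Step 1: is a Beck scale scheduled anywhere?** No. Apart from the Appendix A sentence, the only mention is the title of reference 78.

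**Step 2: could the paragraph on mediational analyses supply one?** It states that depressive symptoms are measured more often than the 3 of 8 post-baseline visits at which the PHQ is listed. It names no scale, and neither the visit lists nor the table adds a depression scale at the other visits. It therefore supports a baseline measurement, in line with the table, but does not put a Beck form into the schedule.

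**Step 3: which part of the rule is affected?** One of two triggers. Patient report stands. The closing referral sentence also stands, because it depends on no instrument.

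**Step 4: what else could bring low mood to attention?**
- "Adverse Effects Inhaler & Adverse Events" is on the list at each of Visits 1 to 6.
- The MNWS is given at most visits. The documents do not list its items, but they count depressed mood among withdrawal symptoms.
- The study design section says: "Nurses will be closely supervised by a psychologist with extensive expertise in smoking cessation."
- The section on training of counsellors keeps the trainer available to follow up psychological issues and referrals.

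**Step 5: who would apply a PHQ trigger?** The research nurse is the named assessor at Visits 2, 5 and 6, but at Visit 6 the back-up plan allows other staff. A corrected rule should therefore not depend on the nurse administering the form.

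The documents give no basis for estimating how many referrals might be missed.

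**The case against.** The strongest reply is that this is a wrong instrument name and nothing more. The protocol has one depression scale, says that it can follow mood over time and repeats it at three visits. Staff would naturally read the trigger against that scale. Women with suicidal ideation, other severe acute psychiatric symptoms or an unstable psychiatric disorder are excluded, as are those with five or more PHQ items at the specified frequency. The routes in step 4 remain. Most of this stands, and it is why the point is minor. It does not remove the mismatch: the protocol does not say that PHQ worsening sets off the contact, and a sentence that tells sites what to do should name the form they hold.

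A second reply is that the data and safety monitoring plan and the attached surveys are cited but were not supplied, and either may hold a PHQ rule. That is fair. It limits the finding to the supplied text and the sentence as written. Even if a Beck form were among the surveys, no visit in the supplied schedule provides for it.

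A third reply is that naming the PHQ still leaves worsening without a numerical threshold. That is true, but the present sentence has none either. The sponsor may add one, though removing the mismatch does not require it.

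A reader might go further and infer that the trial has no working response to depression, or that women went without referral. The documents support neither inference: patient report and the general referral sentence operate without any scale, and nothing supplied bears on what happened in practice.

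**Conclusion.** The point holds as a minor internal inconsistency in a participant-safety rule. The scored trigger names a scale scheduled at 0 of 10 visits, while the PHQ, collected at 3 of 8 visits after baseline, is not explicitly tied to the action. One of two triggers in one sentence is affected. Randomisation, sample size and the efficacy analyses are untouched.

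Confidence is high that the wording and the schedule disagree. Whether a PHQ rule exists elsewhere depends on documents not supplied.

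**What to change.** In Appendix A, item 2, part B, point 6, replace the Beck questionnaire with the PHQ. State that worsening from the screening or baseline PHQ at Visit 2, 5 or 6, whoever administers it, leads to the counsellor contact and referral already described. If the data and safety monitoring plan or the attached surveys already contain a PHQ rule, cross-reference it instead.

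This is a one-line change with no new form, visit or analysis. The cost is possibly a few more referrals to the counsellor whom the plan already provides.
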